Clinical and safety assessment will occur at week 4 (± 5 days) after randomization. This will use a structured CRF at an in-hospital/clinic assessment or a telephone assessment if the patient is discharged and unable to attend clinic.

- Clinical and safety assessment by study nurse / physician, specifically evaluating adverse events related to the intervention.
- Data collection at visit:
 - o Interim medical history with focus on infectious diseases
 - o Concomitant medication
 - o Significant changes in diet
 - o Changes in stool consistency (Bristol Stool Scale) and frequency
 - o Clinical evaluation using standard, structured assessment
 - o Vital signs [if in-patient]: Temperature, heart rate, blood pressure, weight (will be obtained from medical record, if available, rather than collected specifically for research purposes), waist circumference, respiration rate, oxygen saturation
 - o General health status
 - o Adverse events (NIH criteria)
- Stool collection for 16S sequencing and ARB PCR

C.7.3.4 Visit 6 - Month 6 (± 14 days)

Safety follow-up will occur at month 6 (± 14 days) (structured telephone questionnaire) after randomization.

- Clinical and safety assessment by study nurse / physician, specifically evaluating adverse events related to the intervention.

- Data collection at visit:
 - Interim medical history with focus on infectious diseases
 - Concomitant medication
 - Significant changes in diet
 - Changes in stool consistency (Bristol Stool Scale) and frequency
 - Clinical evaluation using standard, structured assessment
 - General health status
 - Adverse events (NIH criteria)

C.7.4 Early Termination Visit

In the case of an early termination, study staff will complete an 'Early Termination CRF', if possible, and the following will be assessed:

- Clinical and safety assessment by study nurse / physician, specifically evaluating adverse events related to the intervention.
- Data collection at visit:
 - Interim medical history with focus on infectious diseases
 - Concomitant medication
 - Significant changes in diet
 - Changes in stool consistency (Bristol Stool Scale) and frequency
 - Clinical evaluation using standard, structured assessment
 - Vital signs [if in-patient]: Temperature, heart rate, blood pressure, weight (will be obtained from medical record, if available, rather than collected specifically for research purposes), waist circumference, respiration rate, oxygen saturation
 - General health status

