- **Grade 3, Severe:** Severe or medically significant but not immediately life-threatening; hospitalization or prolongation of hospitalization indicated; disabling; limiting self-care ADL.
- **Grade 4, Life threatening:** Places the patient or subject at immediate risk of death. It does not include an adverse event that, had it occurred in a more severe form, might have caused death.
- **Grade 5, Death**

C.8.3 Relatedness

All adverse events, regardless of relatedness should be reported. All adverse events should be evaluated for relatedness when reporting and documenting on the CRF.

The following guidelines of relatedness are used modified from the NIH guidelines:

Related: The adverse event is related to the FMT material – i.e. an event that follows a reasonable temporal sequence from administration of the FMT material, follows a known or expected response pattern to the FMT material, that is

confirmed by improvement on stopping and reappearance of the event on repeated exposure and that could not be reasonably explained by the known characteristics of the patient's clinical state.

Not Related: The adverse event is not related to the FMT material. - i.e. another cause of the event is most plausible; and/or a clinically plausible temporal sequence is inconsistent with the onset of the event and the study intervention and/or a causal relationship is considered biologically implausible.

C.8.4 Solicited Adverse Events after FMT

In addition to open-ended questions on adverse events meeting the above definitions, specific potential adverse events will be inquired about during the follow up period (following intervention through to 6 months after randomization):

Symptom that is clinically more severe than participant's baseline	Severity				
	Grade 1	Grade 2	Grade 3	Grade 4	Grade 5
Fever*	38.0 - 39.0 degrees C (100.4 - 102.2 degrees F)	>39.0 - 40.0 degrees C (102.3 - 104.0 degrees F)	>40.0 degrees C (>104.0 degrees F) for <=24 hrs	>40.0 degrees C (>104.0 degrees F) for >24 hrs	Death
Diarrhea	Increase of <4 stools per day over baseline pre-FMT; mild increase in ostomy output compared to baseline	Increase of 4 - 6 stools per day over baseline; moderate increase in ostomy output compared to baseline; limiting instrumental ADL	Increase of >=7 stools per day over baseline; incontinence; hospitalization indicated; severe increase in ostomy output compared to baseline; limiting self-care ADL	Life-threatening consequences; urgent intervention indicated	Death

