Vomiting	1 - 2 episodes (separated by 5 minutes) in 24 hrs	3 - 5 episodes (separated by 5 minutes) in 24 hrs	>=6 episodes (separated by 5 minutes) in 24 hrs; tube feeding, TPN	Life-threatening consequences; urgent	Death

			or hospitalization indicated	intervention indicated	
Abdominal Pain	Mild pain	Moderate pain; limiting instrumental activities of daily life	Severe pain; limiting self care activities of daily life	n/a	n/a
Bloating	No change in bowel function or oral intake	Systemic, decreased oral intake; change in bowel function	n/a	n/a	n/a
Constipation	Occasional or intermittent symptoms; occasional use of stool softeners, laxatives, dietary modification, or enema	Persistent symptoms with regular use of laxatives or enemas indicated; limiting instrumental activities of daily life	Symptoms interfering with self-care activities of daily life; obstipation with manual evacuation indicated	Life-threatening consequences (e.g. obstruction, toxic megacolon); urgent intervention indicated	Death

* Participants will be given a digital thermometer at the time of enrollment.

C.8.5 Serious Adverse Events

An adverse event or suspected adverse reaction is considered “serious” if, in the view of either the site PI or lead PI, it results in any of the following outcomes:

- Death
- Life-threatening adverse event*
- Inpatient hospitalization or prolongation of existing hospitalization
- A congenital anomaly/birth defect
- Persistent or significant disability or incapacity or substantial disruption of the ability to conduct normal life function
- Important medical events that, may not result in death, be life-threatening, or require hospitalization may be considered when, based

upon appropriate medical judgement, they may jeopardize the patient or subject and may require medical or surgical intervention to prevent one of the outcomes listed in this definition

**Life-threatening adverse event. An adverse event is considered “life-threatening” if, in the view of either the site PI or lead PI, its occurrence places the patient or participant at immediate risk of death. It does not include an adverse event which, had it occurred in a more severe form, might have caused death.*

Any adverse event or suspected adverse reaction that meets the criteria for serious adverse event will be:

- recorded on the appropriate SAE CRF
- followed through resolution by a study clinician
- reviewed and evaluated by a study clinician

C.8.6 Unsolicited Adverse Events

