For non-serious adverse reactions (definitely related, possibly related, not related) the site PI will complete a report and submit it to the medical monitor and lead PI. All non-serious adverse reactions will be reviewed by the DSMB every 6 months or *ad hoc* depending on the clinical case at the discretion of the site PI, study medical monitor and lead PI.

In accordance with safety requirements, the site PI will inform the local IRB and lead PI and will make sure that the involved persons will obtain adequate information. The following instructions must be heeded:

- In the case of an intolerable SAE, the study patient must, at the decision of the site PI, be withdrawn from further treatment/placebo, and symptomatic treatment must be administered. The participant may opt to voluntarily providing sample for duration of study.
- The measures taken must be recorded on the CRF.
- In accordance with local legislation, the site PI will submit copies of the final SAE-report to the Regulatory Authorities concerned, if necessary.

C.8.8 Follow-up of Participants after Adverse Events

AEs will be followed until resolution or stability even if this extends beyond the study-reporting period. Resolution of an AE is defined as the return to pretreatment status or stabilization of the condition with the expectation that it will remain chronic.

Follow-up procedures, evaluations, and outcomes will be recorded on the participant's case report forms.

C.8.9. Halting Rules

C.8.9.1 Study Halting Rules

Enrollment and administration of study intervention will be suspended pending a safety review by the DSMB to determine whether the study will be terminated or re-initiated in the following situations:

Three or more of the randomized participants in a study treatment group have a Grade 3 AE of the same organ system deemed related to the study intervention.

Any serious adverse event of an enrolled participant related to the study intervention including transmission of a pathogen from donor to recipient. An overall pattern of symptomatic, clinical, or laboratory events that the Medical Monitor considers related to study product and that may appear minor in terms of individual events, but that may collectively represent a serious potential concern for safety.

CBER will be notified of any study halt that occurs as a result of any of the above halting criteria.

C.8.9.2 Individual's Halting Rules

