	Screening ¹ (Visit 1)	Enrollment ¹ and FMT (Visit 2)	Follow-Up Visit Day 3 (Visit 3)	Follow Up Visit Day 10 (Visit 4)	Follow Up Visit Week 4 (Visit 5)	Follow Up Visit Month 6 (Visit 6)
Identified positive VRE stool sample	X					
Informed consent	X (if active screening)	X				
Baseline medical assessment		X				
Adverse events			X	X	X	X
Clinical and Safety Assessment ²		X	X	X	X	X
Test capsule		X (as part of eligibility)				
FMP-402 or placebo		X				
Stool sample ³		X	X	X	X	
ARB PCR testing		X	X	X	X	

1. Females of childbearing potential will undergo urine pregnancy test the day of intervention and participants that are at risk for EBV/CMV associated disease (at investigator's discretion, e.g. immunocompromised) will undergo EBV and CMV IgG testing, if double positive status (EBV+/CMV+) not already documented. If either is negative, the patient will be excluded.
2. Clinical and Safety Assessment may be in-hospital/clinic or telephone if the patient is discharged and unable to attend clinic
3. Stool samples (or rectal swab per standard of care for VRE) may also be collected at time of VRE infection.

C.17.3 NIH Common Terminology Criteria for Adverse Events (CTCAE)
Adverse Events Recording Form

Record of adverse events:				
System:	Present	Grade	Attribute	Describe reaction (refer to appendix 9)
Systemic				
Infection				
Injection site reaction				
Skin/dermatologic				
Cardiovascular				
Gastrointestinal				
Neurologic				
Respiratory				
Musculoskeletal				
Genitourinary				
Ocular/Visual				
Endocrine/metabolic				
Laboratory AE:				
Hematologic				
Chemistry				
Urinalysis				

NIH Adverse Event Severity Grading Scale*	
Scale	Description
1	Mild
2	Moderate
3	Severe
4	Potentially life-threatening
5	Death

NIH Adverse Event Relatedness *	
Likely	Description
Definitely related	The adverse event is related to the FMT material – i.e. an event that follows a reasonable temporal sequence from administration of the FMT material, follows a known or expected response pattern to the FMT material, that is confirmed by improvement on stopping and reappearance of the event on repeated exposure and that could not be reasonably explained by the known characteristics of the patient's clinical state.

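### The first halting trigger counts Grade 3 events only, so a related fever that becomes Grade 4 by lasting past 24 hours can drop out of the count

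*Combined protocol and SAP*

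**What the plan says.** C.8.9.1 gives three situations in which enrollment and dosing stop pending DSMB review.

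- **Trigger 1** is a count: "Three or more of the randomized participants in a study treatment group have a Grade 3 AE of the same organ system", provided that these events are judged related. It is the only trigger that names a grade or a number.
- **Trigger 2** depends on seriousness, not grade: "Any serious adverse event of an enrolled participant related to the study intervention".
- **Trigger 3** is a pattern of events that the Medical Monitor considers related and of collective concern.

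C.8.2 describes Grade 4 as life threatening: "Places the patient or subject at immediate risk of death". C.8.5 uses nearly the same words for a life-threatening serious event: "its occurrence places the patient or participant at immediate risk of death", in the view of either the site PI or the lead PI. Grade 4 is not itself on the C.8.5 list of serious outcomes. That list also has a category of important medical events, which depends on medical judgement.

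In the C.8.4 table, fever above 40.0 C is Grade 3 up to 24 hours. The Grade 4 cell reads ">40.0 degrees C (>104.0 degrees F) for >24 hrs". The Grade 4 cells for diarrhea, vomiting and constipation require life-threatening consequences; abdominal pain and bloating have no Grade 4. The C.17.3 recording form labels Grade 4 only as "Potentially life-threatening". C.8.7 records severity and seriousness as separate items.

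**The concern.** A halting rule should not become harder to meet as an event gets worse. Read literally, trigger 1 does this for one solicited symptom. A related fever above 40.0 C adds one to the count if it ends within 24 hours and nothing if it lasts longer.

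The protocol leaves room for a Grade 4 fever that is not classed as serious. C.8.4 states "Participants will be given a digital thermometer at the time of enrollment", and after discharge the week 4 contact may be "a telephone assessment if the patient is discharged and unable to attend clinic"; C.7.3.1 allows the same at day 3. A fever can therefore be graded from readings and hours, with no hospital stay and no finding of immediate danger to life.

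Fever is a relevant signal here. C.2.3.1 lists fever and bacteremia among the infectious risks of FMT, and C.8.1 gives newly acquired bacteremia as its example of an event of special interest. Each participant is dosed once, so a halt protects those not yet dosed.

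**Working it through.** The plan states no figure for this rule, so there is none to reproduce. The check has two parts.

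**1. Tracing the rule.** Take three participants in one group with fevers above 40.0 C, all deemed related and recorded under one organ system. (The C.17.3 form has both a systemic and an infection row, so the last condition is an assumption.) Suppose neither PI judges any of them serious under any C.8.5 criterion, including important medical events.

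| Grades | Example durations | Trigger 1 count as written | Met? | Count with 'or higher' | Met? |
|---|---|---|---|---|---|
| 3-3-3 | 20, 20, 20 h | 3 | yes | 3 | yes |
| 3-3-4 | 20, 20, 30 h | 2 | no | 3 | yes |
| 4-4-4 | 30, 30, 30 h | 0 | no | 3 | yes |

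If either PI judges one of these related fevers serious, trigger 2 applies and the gap disappears. The same holds for a fever leading to admission or a longer stay. A Grade 5 event is a death, hence serious, so trigger 2 covers it if related.

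**2. How long the gap could last if nobody acts.** Inputs: 46 participants and 11 months to enroll (Protocol Summary); DSMB reports at about 50% enrollment and every 6 months (C.14.4). Assumptions: even enrollment, and a start date for the 6-monthly clock, which the protocol does not give.

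- Enrollment rate: 46 / 11 = 4.18 per month.
- 50% report: 23 participants, at 23 / 4.18 = month 5.5.
- Clock starting at first enrollment: 6-monthly report at month 6; the next, at month 12, falls after enrollment ends.
- Before month 5.5: three affected participants are already enrolled, so at most 23 − 3 = 20 more.
- After month 6: 11 − 6 = 5 months, 46 × 5 / 11 = 20.9 more.
- Longest wait: 20.9 participants, of whom 20.9 / 2 = 10.5 on FMP-402 under 1:1 allocation.

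If the clock starts x months before first enrollment, the 6-monthly reports fall at months 6 − x and 12 − x:

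| x | Reports during enrollment (month) | Longest interval (months) | Participants (interval × 46/11) |
|---|---|---|---|
| 0 | 5.5, 6 | 5.0 | 20.9 |
| 0.5 | 5.5 | 5.5 | 23.0 |
| 1 | 5, 5.5, 11 | 5.5 | 23.0 |
| 2 | 4, 5.5, 10 | 4.5 | 18.8 |
| 3 | 3, 5.5, 9 | 3.5 | 14.6 |
| 3.5 | 2.5, 5.5, 8.5 | 3.0 | 12.5 |
| 4 | 2, 5.5, 8 | 3.5 | 14.6 |
| 5 | 1, 5.5, 7 | 4.5 | 18.8 |

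For a clock starting up to 5 months early, the longest wait is therefore about 12.5 to 23 participants. These are ceilings: they need the third fever to fall just after a report and every earlier route to action to go unused.

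**The case against.** The strongest reply is that Grade 4 already means life threatening in C.8.2, so a recorded Grade 4 fever would be serious, and one such related event fires trigger 2. Either PI's view is enough, and the important-medical-events category offers a further route without admission or immediate danger. This stands for most Grade 4 events and makes the gap small. It does not close it: the fever cell sets its own criterion of temperature and hours, and both routes to seriousness depend on someone's judgement.

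A second reply is that a 30-hour fever was Grade 3 for its first 24 hours, or that Grade 3 is plainly meant as a minimum. The text says neither. If a minimum is the intent, the edit only records it.

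A third is that the definition of relatedness in C.8.3 asks for reappearance on repeated exposure, which a single dose cannot show, so on a strict reading hardly any event qualifies. That is a fair criticism of C.8.3, but it affects triggers 1 and 2 alike and does not justify counting a worse event as less.

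A fourth is that other safeguards exist. This stands. The site PI reports every non-serious reaction to the medical monitor and lead PI (C.8.7), so the person who can invoke trigger 3 receives each fever. The PIs can halt the study (C.5.3.5), ad hoc DSMB review is possible, and participants keep a diary and are told to seek care if indicated (C.8.6). Each needs someone to act.

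Two stronger readings are tempting. A reader might infer that Grade 4 events in general escape the halting rules; trigger 2 and the C.8.2 definition show otherwise. A reader might also infer that the missing words remove an otherwise automatic halt and so expose about 21 participants. The documents do not support that. Trigger 1 itself needs a relatedness judgement and a count within one treatment group, while clinicians are blinded and OpenBiome holds the schedule (C.5.3.2). The DSMB sees assignments in closed session (C.8.10.1), and no count by arm between its meetings is described.

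**Conclusion.** Wrong as written, minor. Taken literally, trigger 1 has a perverse result for fever: 3-3-3 meets the threshold, while 3-3-4 and 4-4-4 do not when no fever is judged serious. The finding rests on the literal wording of trigger 1, on the duration-only Grade 4 fever cell, and on the fevers being related, in one group, under one organ system and non-serious to both PIs.

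The effect is narrow. The documents give no basis for estimating how often this pattern would occur, and the gap is zero if every Grade 4 event is treated as serious. The figure of about 21 further participants (range about 12.5 to 23) is a worst-case wait for a scheduled DSMB report, not an expected harm. It depends on the assumed even enrollment and clock start, and the DSMB charter, which sets review frequency, is not among the documents.

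**What to change.** In the first trigger of C.8.9.1, insert 'or higher' after 'Grade 3', leaving the organ-system and relatedness conditions as they are. Make the same edit in the DSMB charter if it repeats the rule.

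The cost is two words; data collection, endpoints and sample size do not change. The downside is an occasional earlier pause for DSMB review. Related Grade 4 events judged serious already halt the trial, so extra pauses arise only when three or more participants in one group have related events of Grade 3 or higher in one organ system, at least one of them a non-serious Grade 4, and the Grade 3 events alone fall short of three.

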VRE	Vancomycin Resistant Enterococcus

< This page is intentionally left blank >

PROTOCOL SUMMARY

Title:	A Randomized Controlled Trial of Encapsulated Fecal Microbiota for Vancomycin Resistant Enterococcus Decolonization
Phase:	II
Population:	Vancomycin resistant enterococcus (VRE) identified by stool culture in the past 14 days among adults.
Sample size	46 (1:1 randomization) - 23 in the treatment group and 23 in the placebo group).
Number of sites:	Multi-center study at 2 tertiary academic medical centers (Indiana University and University of Wisconsin).
Study duration:	Approximately 1 year.
Description of Agent:	Encapsulated fecal microbiota preparation (formulation FMP-402). Please refer to OpenBiome BBMF # 17300, Section I, H. Sourced from human-derived microbes. Please refer to OpenBiome BBMF # 15543, Section F.

Study Objectives: To investigate the efficacy and safety of FMP-402 to decolonize VRE.

Primary Objectives:

- To determine the VRE decolonization rate of FMP-402 versus placebo.
- To evaluate the safety profile for FMP-402 versus placebo.

Secondary Objectives:

- To determine the VRE infection rate of FMP-402 versus placebo.
- To evaluate the decolonization rate of antibiotic resistant bacteria (ARB) for FMP-402 versus placebo.
- To determine the composite ARB infection rate for FMP-402 versus placebo.
- To evaluate the time to VRE colonization and infection.
- To evaluate the VRE decolonization rate for FMP-402 versus placebo among immunocompromised patients.
- To evaluate VRE decolonization rate for FMP-402 versus placebo among those 65 years and older.

Exploratory Objectives:

- To evaluate the microbiome disruption index (MDI) by 16s rRNA sequencing): MDI-community and MDI-species (day 3, day 10, week 4).
- To evaluate the trends in VRE type/strain-level engraftment using whole genome sequencing among those colonized.

**Study
Endpoints/Outcome
Measures:**

Primary Efficacy Outcome Measure:

- Proportion of participants with VRE decolonization at day 10 (± 3 days) after randomization.
 - VRE decolonization is defined by absence of VRE on stool culture using standard clinical laboratory techniques.

Secondary Efficacy Outcome Measures:

- Proportion of participants with VRE infection at day 3 (± 2), day 10 (± 3), week 4 (± 5 days) after randomization.
 - VRE infection will be defined as an associated bacteremia, urinary tract infection, or wound-related infection.

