Secondary Objectives:

- To determine the VRE infection rate of FMP-402 versus placebo.
- To evaluate the decolonization rate of antibiotic resistant bacteria (ARB) for FMP-402 versus placebo.
- To determine the composite ARB infection rate for FMP-402 versus placebo.
- To evaluate the time to VRE colonization and infection.
- To evaluate the VRE decolonization rate for FMP-402 versus placebo among immunocompromised patients.
- To evaluate VRE decolonization rate for FMP-402 versus placebo among those 65 years and older.

Exploratory Objectives:

- To evaluate the microbiome disruption index (MDI) by 16s rRNA sequencing): MDI-community and MDI-species (day 3, day 10, week 4).
- To evaluate the trends in VRE type/strain-level engraftment using whole genome sequencing among those colonized.

C.3.2 Study Outcome Measures**C. 3.2.1 Efficacy Outcome Measures****Primary Efficacy Outcome Measure:**

- Proportion of participants with VRE decolonization at day 10 (± 3 days) after randomization.
 - VRE decolonization is defined by absence of VRE on stool culture using standard clinical laboratory techniques.

Secondary Efficacy Outcome Measures:

- Proportion of participants with VRE infection at day 3 (± 2), day 10 (± 3), week 4 (± 5 days) after randomization.
 - VRE infection will be defined as an associated bacteremia, urinary tract infection, or wound-related infection.
- Proportion of participants with other antibiotic resistant bacteria (ARB) colonization at day 10 (± 3) after randomization. ARB testing will be conducted with Acuitas™ MDRO test (OpGen) or similar PCR assay platform.
 - ARB will be defined as: a) carbapenem-resistant enterobacteriaceae (CRE) by PCR; b) extended-spectrum beta-lactamase (ESBL) producing organism by PCR; c) *C. difficile* by PCR.
- Proportion of participants with antibiotic resistant bacteria (ARB) colonization at day 10 (± 3) after randomization. ARB testing will be conducted with AcuitasTM MDRO test (OpGen) or similar PCR assay platform.
 - ARB will be defined as: a) carbapenem-resistant enterobacteriaceae (CRE) by PCR; b) extended-spectrum beta-lactamase (ESBL) producing organism by PCR; c) *C. difficile* by PCR; d) VRE

- Proportion of participants with composite ARB infection at day 3 (± 2), day 10 (± 3), week 4 (± 5 days) after randomization and time (in days) when ARB infection occurs.

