Protocol violation/non-compliance

Pregnancy

Lost to follow up

Other (must be noted)

C.5.3.4 Handling Withdrawals

The primary reason for withdrawal from the study will be recorded on the Study Status CRF page. Participants will be encouraged to complete the Early Termination Visit. The Early Termination Visit procedures are listed. Although participants are free to withdraw at any time, participants will be encouraged to remain in the study for follow-up safety evaluation. Every attempt should be made to follow all AEs and SAEs ongoing at the time of early withdrawal to resolution or until stabilized. If possible, a final stool sample will be collected at the Early Termination Visit. Intention-to-treat analysis will be utilized according to best practices in clinical trials. Attempts will be made to complete safety follow-up for all subjects who have received the study product, including those who have discontinued participation in other study procedures, for the duration of the planned follow-up period.

Participants who are withdrawn from the study after randomization but before intervention or placebo will be replaced. Possible reasons for participant withdrawal after randomization include but are not limited to:

- Participants who are started on a new course of antibiotics after randomization and before intervention/placebo
- Unrelated participant death

C.5.3.5 Termination of Study

In the unlikely event that significant safety concerns arise, the PIs can terminate or halt the study pending review by the DSMB. In addition, this study may be halted early based on the DSMB charter or FDA recommendations.

C.6. STUDY INTERVENTION/INVESTIGATIONAL PRODUCT

C.6.1 Study Product Description

FMP-402 is encapsulated fecal microbiota sourced from human-derived microbes. The human source generating the fecal microbes has been extensively screened for infectious pathogens and microbiome mediated diseases using a standardized process (found in OpenBiome's BBMF # 15543, Section F). Additionally, the capsule delivery vehicle enables targeted deposition of the investigational active pharmaceutical ingredient into the colon.

C.6.2 Formulation

C.6.2.1 Encapsulated fecal microbiota preparation (formulation FMP-402)

This formulation is encapsulated fecal microbiota sourced from human-derived microbes generated by healthy, screened donors, as described in OpenBiome's [REDACTED]

BBMF # 17300

C.6.2.2 Placebo

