The site principal investigator (PI) (or designee) will maintain an accurate record of the receipt of the investigational materials as shipped, including the date received. One copy of this receipt will be returned to OpenBiome when the contents of the investigational materials shipment have been verified. In addition, the unblinded laboratory technician based at OpenBiome will maintain a log of all clinical trial materials (FMP-402 and placebo) dispensed. This clinical trial material accountability record will be available for inspection at any time.

C.6.6 Modification of Study Intervention/Investigational Product for a Participant

If the participant is unable to complete the full dose of FMP-402 or placebo, the following modification will take place. The dose will be recorded and the remainder of capsules will be offered to participant the same day at the discretion of the treating physician. Intention-to-treat analysis will be utilized according to best practices in clinical trials.

C.6.7 Assessment of Participant Compliance with Study Intervention/Investigational Product

FMP-402 or placebo capsules will be consumed under direct supervision of study staff.

C.6.8 Concomitant Medications/Treatments

Given the participants with VRE colonization and who are most at risk for VRE infection are patients with multiple comorbidities, all medications will be accepted in this study, at the discretion of the treating physician. This includes, but is not limited to:

1. Anti-hypertensive therapies
2. Heart failure medications
3. Diuretics
4. Laxatives
5. Topical medications
6. Anti-depressants
7. Statins
8. Diabetic medication

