Monitoring visits will include, but are not limited to, review of regulatory files, accountability records, eCRFs, informed consent forms, medical and laboratory reports, and protocol compliance. Study monitors will meet with site PIs to discuss any problems and actions to be taken and document visit findings and discussions.

C.10. STATISTICAL CONSIDERATIONS

This is a randomized double blind, placebo controlled clinical trial to determine the safety and efficacy of FMP-402 on the decolonization of VRE.

C.10.1 Sample Size

Sample size (n=46) was calculated based on a conservative estimate of 85% decolonization in FMT group, 40% in control group with power=0.9 and alpha=0.05 in keeping with preliminary data and a conservative 15% drop-out rate.

C.10.2 Final Analysis Plan

Categorical data will be described using descriptive statistics (proportions and percentages). Continuous data will be described using means and standard deviations (normally distributed data) or using medians and interquartile range (non-parametric data). Appropriate comparative statistical tests will be chosen based in the variable types (categorical, dichotomous, continuous) and distribution (parametric, non-parametric) and will be used to describe significant differences between intervention and control groups. Where appropriate, point estimates and confidence intervals will be reported. The p-value will be two tailed with a significance level of 0.05.

C.11. SOURCE DOCUMENTS AND ACCESS TO SOURCE DATA/DOCUMENTS

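### The power of 0.90 in C.10.1 is an approximation that the design does not deliver: with 15% of day-10 cultures missing, exact power is about 0.87 by chi-square or 0.78-0.83 by Fisher

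*Combined protocol and SAP*

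**What the plan says.** C.10.1 is a single sentence that bases n=46 on "85% decolonization in FMT group, 40% in control group with power=0.9 and alpha=0.05 in keeping with preliminary data and a conservative 15% drop-out rate". The Protocol Summary divides the total as "23 in the treatment group and 23 in the placebo group". C.10.1 names no test, formula or software, and does not say whether 46 is before or after drop-out.

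C.10.2 sets a two-tailed significance level of 0.05 and otherwise leaves the choice open: "Appropriate comparative statistical tests will be chosen based in the variable types (categorical, dichotomous, continuous) and distribution (parametric, non-parametric").

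The primary endpoint (C.3.2.1) is binary, read at day 10: "VRE decolonization is defined by absence of VRE on stool culture using standard clinical laboratory techniques". On withdrawals, C.5.3.4 says "Intention-to-treat analysis will be utilized according to best practices in clinical trials", and C.6.6 repeats it for incomplete dosing. Neither section says how a missing day-10 culture enters the analysis. C.5.3.4 adds: "Participants who are withdrawn from the study after randomization but before intervention or placebo will be replaced". The only test the documents connect with this kind of outcome is Fisher's exact test, used for the retrospective comparison of 9/9 with 3/7 (C.2.2 and C.16.1).

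**The concern.** A power figure describes a particular test applied to a particular number of outcomes. Here the test is open, and about 39 outcomes are expected if the drop-out occurs before day 10. With samples this small, normal approximations can be several points away from what a test delivers, and chi-square and Fisher can disagree on the same table. If the trial does not reach significance, readers will judge that result against a planned 10% chance of missing an effect of 85% against 40%. If the real chance is nearer 13% or 20%, a negative result carries less weight than the protocol suggests.

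**Working it through.** **Inputs.** Decolonization 0.85 and 0.40, power 0.90, drop-out 15%, total 46 (C.10.1); 23 per arm (Protocol Summary); two-sided 0.05 (C.10.2). Normal quantiles: 1.960 and 1.2816; the square of their sum is 10.507.

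**Step 1: reproduce 46.**

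- Unpooled normal approximation: n = 10.507 × (0.85×0.15 + 0.40×0.60) / 0.45² = 10.507 × 0.3675 / 0.2025 = 19.07 per arm. With drop-out, 19.07/0.85 = 22.43, so 23 per arm, 46 in total.
- The same formula, rounded up first: 20 per arm, 40 in total, and 40 × 1.15 = 46.
- Pooled approximation (mean rate 0.625): n = [1.960×√(2×0.625×0.375) + 1.2816×√0.3675]² / 0.2025 = 22.17, so 23 per arm, 46 in total, with no drop-out allowance. With drop-out, 22.17/0.85 = 26.08, so 27 per arm, 54 in total.

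The stated number is therefore reproduced, by more than one route. On the first route, nominal power at 19.5 per arm is Φ(0.45/√(0.3675/19.5) − 1.960) = 0.906.

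**Step 2: evaluable number.** 46 × 0.85 = 39.1. The cases checked are 38 to 40 evaluable, with arms of 19 or 20.

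**Step 3: exact power.** For each pair of arm sizes, list every possible pair of success counts, apply the test at two-sided 0.05, and add up the binomial probabilities (0.85 and 0.40) of the pairs that reject. Maximum type I error is the largest rejection probability over a common rate in both arms.

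| Evaluable (FMP-402/placebo) | Chi-square | Fisher | Unpooled Wald |
|---|---|---|---|
| 23/23 | 0.913 | 0.853 | 0.922 |
| 20/20 | 0.873 | 0.797 | 0.904 |
| 20/19 | 0.868 | 0.833 | 0.868 |
| 19/20 | 0.868 | 0.817 | 0.888 |
| 19/19 | 0.868 | 0.783 | 0.882 |

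Over 38-40 evaluable, maximum type I error is 5.3-5.8% for chi-square, 2.5-3.6% for Fisher and 6.0-8.1% for Wald. The one entry at 0.90 or above in those rows, Wald at 20/20, is the one with 8.1%. Boschloo's test gives about 0.85 at 20/19 and at 20/20.

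**Step 4: dependence on the loss by day 10.** Letting each arm lose participants at random and averaging the complete-case power:

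| Loss by day 10 | Chi-square | Fisher |
|---|---|---|
| 5% | 0.900 | 0.850 |
| 10% | 0.884 | 0.830 |
| 15% | 0.864 | 0.811 |

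**Step 5: sensitivity scenario only.** Suppose all 46 are analysed and the 15% without a culture are counted as not decolonized. The rates become 0.85×0.85 = 0.7225 and 0.40×0.85 = 0.34. Exact power at 23/23 is then 0.772 (chi-square) or 0.668 (Fisher). The protocol does not state this rule.

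**The case against.** The strongest reply is that C.10.1 does not claim exact power. A standard formula gives 46 from the sponsor's own inputs with drop-out included, and small binary trials often differ from their approximations by a few points. On the 40 × 1.15 route the planned evaluable number is 40, and at 20/20 the matching Wald test does reach 0.904. This stands as far as it goes. A reader might infer that 46 was miscalculated or that drop-out was forgotten; the documents do not support either, because the unpooled route with drop-out gives 46. What the reply does not rescue is the 0.90 itself: the Wald result comes with a maximum type I error of 8.1% against the stated 0.05, and at 20/19 or 19/20 the same test gives 0.868 or 0.888.

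A second stronger reading is that intention-to-treat lowers power to 0.77 or 0.67. Those figures need missing cultures to count as failures. The protocol states the principle but not that rule, so they illustrate one possible rule and do not describe the plan.

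Third, the 15% need not all fall before day 10. Follow-up runs to month 6, and withdrawals before dosing are replaced. At 5% loss by day 10, chi-square power is 0.900 and that gap disappears; Fisher stays at 0.850.

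Finally, a shortfall of 3 points by chi-square is smaller than the uncertainty in the 85% and 40%. That is fair, and it is why the remedy does not change the sample size.

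**Conclusion.** The point holds as a correction to a stated figure. At the plan's own 15% drop-out, none of the tests checked that keeps type I error near 0.05 has exact power of 0.90. The shortfall is about 3 points for chi-square (0.87) and 7-12 points for Fisher (0.78-0.83). The Fisher figure should be given as a range, because it moves by up to 5 points with the arm sizes. With no loss, chi-square delivers the stated power (0.91) and Fisher does not (0.85).

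This rests on the plan's rates of 85% and 40%, on all of the 15% being post-dose and missing at day 10, and on those participants being left out of the analysis. If fewer are missing at day 10 the gap narrows. If missing cultures are counted as failures it widens.

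**What to change.** Keep n=46. Name the primary test in C.10.2, state in C.10.1 the formula that produced 46, and restate the power there for the chosen test:

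- Pearson chi-square: exact power 0.91 if all 46 have a day-10 culture, about 0.87 if 15% are missing at day 10 and excluded.
- Fisher's exact test: 0.85 with no loss, about 0.78-0.83 with 15% loss.

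State the rule for a missing day-10 culture alongside the intention-to-treat statement. If that rule counts missing as not decolonized, add the corresponding power at 15% missing (about 0.77 by chi-square or 0.67 by Fisher). Until a rule is set, those two figures belong only in a labelled sensitivity scenario.

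The cost is wording and a less favourable stated power, with no extra participants. The choice of test remains the sponsor's: at 38-40 evaluable, chi-square can slightly exceed 0.05, while Fisher stays well below it and gives up about 3-9 points of power.
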